5.8 Software Version

All analyses will be performed using SAS® software Version 9.4 or higher.

6 STATISTICAL CONSIDERATIONS

6.1 Adjustments for Covariates

Baseline value for the absolute change from baseline of continuous efficacy parameters will be included as a covariate in the statistical models.

6.2 Handling of Dropouts or Missing data

See Appendix 2 for handling of completely or partially missing dates for prior and concomitant medications and adverse events.

For safety analyses, no imputation of the data will be done and analyses will be conducted on the observed cases (OC). In Part A efficacy analyses will be performed using Mixed Model Repeated Measures (MMRM) analyses as primary analyses to account for missing observations (See section 13.1).

For subjects starting prohibited medications as listed in section 6.4.3 of the protocol, all efficacy data captured after the start of prohibited medication will be considered missing for the analysis of those parameters. A sensitivity analysis on the primary endpoint mTLSS will be done including all efficacy data for these subjects (before and after the prohibited medication).

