At selected study centers, in a subset of approximately 36 subjects who consent, PD blood samples will be collected pre-dose on Day 1 and Week 16 (or ET visit, if applicable and if it occurs prior to Week 16). PD samples will be obtained from the same subjects who consent to biopsy collection. An additional PD blood samples will be collected at Week 4 in subjects who also consent to four skin biopsies.

At selected study centers, in a subset of approximately 36 subjects who consent, three or four skin biopsies will be collected during this study. Two 2.5-mm punch biopsies (one from lesional skin and one from adjacent nonlesional skin) will be collected from the palmar aspect of the hand at Day 1, and one 2.5-mm punch biopsy will be collected from the same lesional skin (outside the scar of the previous biopsy, at least 1 cm away from the previous scar) at Week 16 (or ET visit, if

applicable and if it occurs prior to Week 16). In addition, one 2.5-mm punch biopsy will be collected from the same lesional skin (outside the scar of the previous biopsy, at least 1 cm away from the previous scar) at Week 4 in subjects who consent to four skin biopsies.

For all subjects, on Day 1, and Weeks 4 and 16 (or ET visit, if applicable and if it occurs prior to Week 16), skin samples from of the hand and foot (if subject has presence of foot eczema on Day 1) will be collected using tape stripping technique. During the same visits, skin microbiome samples will be collected from the worst eczema lesion of the hand (palmar aspect, when possible) and worst eczema lesion of the foot (plantar aspect, when possible) (if subject has presence of foot eczema on Day 1). The microbiome sampling must be collected prior to tape stripping and biopsies.

Preferably, all skin sampling (microbiome samples, tape strips and biopsies) should be collected from the same lesion.

At selected study centers, in a subset of approximately 36 subjects who consent, medical photographs of both aspects (palmar and dorsal) of both hands will be taken.

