6.4.3 Prohibited Therapies or Procedures

Table 4 lists prohibited medications are not to be used from the defined washout periods before the first administration of study treatment at the Day 1 visit through the last study visit.

The discretionary use of concomitant treatments or therapies for CHE is prohibited between Day 1 and Week 8 visit. However, after the Week 8 visit, should subjects experience an exacerbation of their CHE that requires, in the opinion of the investigator, the use of a prohibited topical therapy, the following approach should be followed:

1. The investigator needs to discuss the case with the medical monitor in order to obtain permission to use a prohibited medication.
2. Subjects who start prohibited topical medications as a treatment for CHE within the first 8 weeks of the study will be discontinued from the study product (ASN002 or placebo) and will perform the ET visit at the time of discontinuation.
3. Subjects who start prohibited topical medications as a treatment for CHE after the first 8 weeks of the study may continue all the study assessments up to the last study visit. Skin biopsies will not be performed after the start of a topical medication.
4. Subjects who start any other prohibited medications or therapies for other reasons may be withdrawn from the study, at the investigator's discretion in agreement with the medical monitor and the sponsor.

If in any doubt, investigators are advised to discuss medications with the medical monitor.

Table 4. Prohibited Therapies or Procedures

Prohibited medications, products, and procedures	Washout period prior to first dose (Day 1)
Any marketed or investigational biological agent	12 weeks or 5 half-lives (whichever is longer)
Dupilumab	12 weeks
Nonbiological investigational product or device	4 weeks
Live attenuated vaccine	4 weeks
Alitretinoin, isotretinoin, acitretin or other systemic retinoids	4 weeks
Systemic treatments (other than biologics) that could affect CHE (e.g., calcineurin inhibitors, methotrexate, cyclosporine, hydroxycarbamide [hydroxyurea], azathioprine, oral/injectable corticosteroids) Note: Intranasal corticosteroids, eye or ear drops containing corticosteroids, and inhaled corticosteroids for stable medical conditions are allowed	4 weeks
PUVA treatment, UV-B phototherapy (including tanning beds) or excimer laser, excessive sun exposure or has used tanning booths	4 weeks

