Topical treatments that could have an impact on CHE including, but not limited to, topical corticosteroids, topical retinoids, crisaborole, calcineurin inhibitors, tars, bleach, bleach baths, antimicrobials, medical devices.	2 weeks
For subjects consenting to biopsies only: anticoagulant medication, such as heparin, low molecular weight (LMW) heparin, warfarin, antiplatelets (except low-dose aspirin which will be allowed) Note: Nonsteroidal anti-inflammatory drugs (NSAIDs) will not be considered antiplatelets and will be allowed.	2 weeks
Systemic antibiotics	2 weeks
Topical antibiotics Note: Use of topical antibiotics on biopsy site only is allowed.	2 weeks
Topical products containing urea or salicylic acid	1 week

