6.6 Examination of Subgroups

Subgroup analysis by PGA = 3 (moderate) or 4 (severe) will be performed for the primary efficacy endpoint (percent change from baseline in mTLSS) and key secondary endpoints (proportion of patients with reduction in PGA) including inferential statistics as described in section 13.1 and 13.2.

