For categorical efficacy endpoints involving proportions hand PGA, a Cochran Mantel Hansel test (CMH) stratified by baseline PGA will be presented by visit for Part A. Analyses will be based on the mITT population for all secondary parameters and supported by the PP population. Missing data at any post-baseline assessment will be imputed as a non-responder.

Actual values of PaGA will summarized descriptively using frequency and percentage.

Time to response relative to baseline (based on hand PGA) will be compared between treatments using the Kaplan Meier method. A subject will be considered censored if he has not met the event of interest at the end of the study or if the subject is lost to follow up at last observation. Those subjects will be censored at their last available hand PGA assessment.

Descriptive statistics will be presented for all secondary endpoints by visit and treatment group and sorted by Part A.

All endpoints relative Part B for the above assessments are considered exploratory only and will be summarized descriptively by initial treatment group and overall.

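### SAP 6.2 voids efficacy scores after any product on the prohibited list, including ones not tied to hand eczema; the two hand PGA response rates then count failures, and no all-data check covers them (optional, low weight)

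*SAP*

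**What the plan says.** **Trigger and consequence.** SAP section 6.2 applies to subjects starting any medication listed in protocol section 6.4.3. From that start, "all efficacy data captured after the start of prohibited medication will be considered missing for the analysis of those parameters". Indication, relevance to CHE and duration set no limit. Protocol section 9.3.1 leaves this handling to the SAP, so nothing elsewhere narrows it.

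**The list.** Some rows of protocol Table 4 are expressly for treatments that could affect CHE. Others carry no such link. One is "Live attenuated vaccine". Another begins "For subjects consenting to biopsies only: anticoagulant medication, such as heparin". The biopsy subset is limited: "in a subset of approximately 36 subjects who consent, three or four skin biopsies will be collected during this study" (protocol section 4.1). Systemic antibiotics also have their own row.

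**Staying in the study.** Protocol section 6.4.3, item 4, treats use for reasons other than CHE separately: "Subjects who start any other prohibited medications or therapies for other reasons may be withdrawn from the study". Withdrawal is at discretion, so visits and scoring can continue.

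**PGA proportions.** For the categorical hand PGA endpoints, SAP section 13.2 adds: "Missing data at any post-baseline assessment will be imputed as a non-responder". SAP section 6.6 counts such proportions among the "key secondary endpoints (proportion of patients with reduction in PGA").

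**Planned check.** SAP sections 6.2 and 13.1 restore scores after prohibited medication in one sensitivity analysis, for hand mTLSS. SAP section 7.1 will report how many subjects used prohibited therapy up to Week 16.

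**The concern.** Table 4 is a list for trial conduct. SAP section 6.2 uses it as a list of events that invalidate efficacy scores, and the two purposes do not coincide. The anticoagulant row shows this most clearly: the same drug voids the later scores of a subject who consented to biopsies and leaves those of any other subject intact, although biopsy consent has no bearing on whether a PGA score is valid.

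The continuous endpoints in the MMRM lose less, because scores before the product still inform Week 16. In the PGA proportions a voided score becomes a definite failure, whatever was observed. The sponsor planned an all-data check for mTLSS but not for the endpoints where the rule acts most strongly.

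At stake is the reading of the two hand PGA response rates. Equal use across arms shrinks the difference; unequal use can move it either way. The SAP section 7.1 count would show that the rule was triggered, but not what it did to these rates.

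**Working it through.** **1. Arm size.** The plan's figure reproduces. With means 0/25/35, SD 39 and 25 per group, the noncentrality is 25 × (20² + 5² + 15²)/39² = 25 × 650/1521 = 10.7, and the F test has 82.5% power against the stated 80%. Dropout of 25% gives 25/0.75 = 33.3 and dropout of 30% gives 25/0.70 = 35.7, which fits up to 35 per group. I use 35 per arm.

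**2. One subject.** A reclassified responder moves the arm's rate by 1/35 = 2.9 percentage points. A product started at Week 3 voids all four Part A PGA endpoint visits (Weeks 4, 8, 12 and 16); one started at Week 9 voids two (Weeks 12 and 16).

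**3. Biopsy subset.** 36/3 = 12 per arm, if stratification on biopsy collection balances it.

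**4. Equal use, one expected user per arm.** The documents give no PGA response rates, so three pairs are assumed. If use is unrelated to response, a true rate p becomes p × 34/35. Power is for the CMH test stratified by baseline PGA, 35 per arm, strata of 10 moderate and 25 severe (30% of 35 = 10.5), two-sided 0.05, by simulation with 1,000,000 replicates. The last column first multiplies both rates by 0.725, because dropout (27.5%, the middle of the plan's range) also counts as non-response. Losses are from unrounded values.

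| Assumed rates | Difference | Power, no other missing data | Power with 27.5% dropout |
|---|---|---|---|
| 10% vs 35% | 25.0 → 24.3 | 73.1% → 71.5% (loss 1.6) | 56.4% → 55.0% (loss 1.4) |
| 15% vs 45% | 30.0 → 29.1 | 80.4% → 78.6% (loss 1.8) | 61.2% → 59.5% (loss 1.7) |
| 20% vs 50% | 30.0 → 29.1 | 76.5% → 74.7% (loss 1.8) | 55.9% → 54.2% (loss 1.8) |

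**5. Larger or unequal use, illustration only, at 15% vs 45%.**
- Four users in each arm: 30 × 31/35 = 26.6 points, power about 73%.
- One placebo and four drug users: 0.45 × 31/35 − 0.15 × 34/35 = 25.3 points, power about 67 to 68%.
- Four placebo users and one drug user: 0.45 × 34/35 − 0.15 × 31/35 = 30.4 points, so the difference rises slightly.

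Nothing in the documents points to use at these levels or to a split by arm. Four users is 4/35 = 11% of an arm or, if all were anticoagulant users, 4/12 = a third of its biopsy subset.

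**The case against.** **Exposure is narrow.** Exclusion criterion 30 bars anyone planning a live attenuated vaccine during the study, and criterion 46c bars biopsy subjects on anticoagulants in the 2 weeks before Day 1. Under protocol section 4.4.2 a venous thromboembolic or major cardiovascular event ends participation, so scores after it would be missing under any rule. Only unplanned new use remains for the two clear examples. This stands, and it is the main reason for the low weight.

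**Most other rows are relevant, or could be.** Many concern treatments that could act on skin. Antibiotics are a judgement: Table 4 names, among topical treatments that could have an impact on CHE, "calcineurin inhibitors, tars, bleach, bleach baths, antimicrobials, medical devices". Section 4.4.1 requires interruption for oral anti-infectives only beyond 2 weeks, so a shorter course during continued dosing is conceivable. I do not count it as a clear case.

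**A fixed rule is a legitimate choice.** It avoids product-by-product judgement, and failure is a defensible outcome for subjects who needed another CHE treatment. This also stands, but it does not explain why the check on the rule stops at mTLSS.

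**Other analyses might fill the gap.** They do not. The per-protocol analysis drops subjects with major deviations and restores no voided score.

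**Stronger readings to avoid.** A reader might infer that the primary result is compromised. The documents do not support that: the MMRM keeps earlier scores and the all-data mTLSS analysis is planned. A reader might infer that every PGA analysis records a failure. Time to response is instead censored at the last available PGA, and non-responder imputation is stated for the categorical endpoints, not for change in PGA. A reader might also infer a bias for or against the drug, but no document suggests that use differs by arm, and biopsy collection is a stratification factor.

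**Conclusion.** The gap is real but small. As written, the SAP can turn an observed hand PGA responder into a non-responder because of a product that the protocol does not link to CHE, and no planned PGA analysis would reveal it. This reaches the two hand PGA proportions at the Part A visits.

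The size is 2.9 percentage points in an arm per reclassified responder and, for one user per arm, about 1.5 to 2 points of nominal power, with or without the planned dropout. That rests on assumed response rates, 35 per arm and use unrelated to response. Ordinary dropout, also imputed as failure, costs far more: at 15% vs 45%, power falls from 80% to 61%. SAP section 6.5 makes the PGA p-values nominal, and actual use cannot be estimated from the documents. The point is optional and worth making because the remedy is nearly free.

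**What to change.** 1. **Main change, SAP sections 6.2 and 13.2.** Repeat the all-data sensitivity analysis for the two hand PGA proportions (at least a 2-grade reduction to clear, almost clear or mild; clear or almost clear) with the same stratified CMH test. Use scores observed after a listed product, and impute non-response only where no score exists. Cost: two reruns of existing programs with one data flag changed.

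2. **Preferable addition, SAP section 6.2.** Limit the set-to-missing rule to listed products used for CHE, or judged able to affect CHE in a blinded medication review completed before Part A lock. Keep the all-data mTLSS analysis. Cost: SAP wording and a short review. The downside is some judgement that a fixed rule avoids; blinding and timing contain it.

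The first change alone also restores scores after CHE treatments, so a shift in the PGA result could come from either kind of product. The second change separates them.

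Both concern data handling only. Which therapies are prohibited, and how subjects are managed, stays as it is.

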6.3 Interim Analysis and Data Monitoring

No Interim analysis has been planned for this study.

PPD	STATISTICAL ANALYSIS PLAN, Version Final 1.0
Protocol Number: ASN002AD-202 V6.0	Sponsor: Asana BioSciences, LLC

The final analyses on efficacy parameters will be done once all patients have finalized their week 16 assessments. All data will be cleaned up to week 16, a database lock of Part A will be performed and final efficacy results will be provided. The efficacy summaries will be updated for additional visits once the Part-B visits are completed; these Part B summaries will be considered exploratory.

6.4 Multicenter Studies

No by center analysis has been planned for this study.

6.5 Multiple Comparisons/Multiplicity

For the primary endpoint of change-from-baseline in hand mTLSS at Week 16, a Hochberg adjustment will be performed to test the two comparisons of interest (40mg vs. Placebo and 80mg vs. Placebo).

Under Hochberg procedure, the comparison proceeds stepwise from the largest p -value to the smallest p -value to compare the k th largest p -value with $0.05/k$, which is the significance level corresponding to the k th largest p -value. The first time a p -value is less than the corresponding significance level, the testing stops and the significance is claimed for the current comparison and subsequent ones that produce smaller p -values than the current one. If all p -values are larger than or equal to the corresponding significance level, none of the doses are statistically different from placebo.

No adjustments will be made to account for multiplicity in secondary endpoints and multiple assessments through time in the same subjects. P-values presented for these endpoints will be nominal p -values.

6.6 Examination of Subgroups

Subgroup analysis by PGA = 3 (moderate) or 4 (severe) will be performed for the primary efficacy endpoint (percent change from baseline in mTLSS) and key secondary endpoints (proportion of patients with reduction in PGA) including inferential statistics as described in section 13.1 and 13.2.

6.7 Analysis Presentation

Subjects will be presented in columns according to their treatment assignment in Part A. In the tables presenting Part B data or combined Part A and Part B data, placebo subjects from Part A

PPD	STATISTICAL ANALYSIS PLAN, Version Final 1.0
Protocol Number: ASN002AD-202 V6.0	Sponsor: Asana BioSciences, LLC

crossed over to ASN002 80 mg will be presented in the placebo/ASN002 80mg column. See Appendix 1 for presentation of treatment groups.

7 STUDY SUBJECTS

7.1 Disposition of Subjects

All subjects who provide informed consent will be accounted for in this study. Subject disposition will be presented separately for part A and part B. The number of subjects screened and subjects rescreened will be presented. Screen failures and the reason for screen failure will be presented for all screened subjects except for those who were rescreened and did not fail the second screening. Moreover, the number of subject randomized included in each population will be presented. Study completion status and the reason for study discontinuation will also be presented. Number of subjects using prohibited therapy on study up to Week 16 are also presented. The percentage of subjects with screen failures will be calculated using the number of subjects screened as denominator. The percentage of screen failure by reasons will be calculated using the number of screen failures as denominator. Otherwise percentages will be calculated using the number of subjects randomized as denominator. Number of days in the study will be calculated as follows and will be summarized:

$$\text{Number of days in study} = \text{Date of completion/discontinuation} - \text{First dose date} + 1$$

A listing of subject's disposition will be provided. Information on first screening for subjects who were rescreened, including the rescreened subject identifier, will be presented under the first screening subject identifier. A listing of subject's randomization information and a listing of subjects included in each of the study populations will also be provided.

7.2 Protocol Deviations

The number of events and the number and percentage of subjects with at least one major protocol deviation will be summarized by deviation category and treatment group using the safety population. A listing of all major protocol deviations will also be provided.

The protocol deviations in the study will be evaluated on a case to case basis and will be categorized as major or minor. A major protocol deviation is defined as any deviation that may affect the efficacy outcome or subject safety or subject's right. Subjects having major protocol deviation will be finalized prior to the data base lock.

PPD	STATISTICAL ANALYSIS PLAN, Version Final 1.0
Protocol Number: ASN002AD-202 V6.0	Sponsor: Asana BioSciences, LLC

Following are some potential major protocol deviations.

- Violation of major Inclusion /Exclusion Criteria Assessment
- Treatment compliance of <80% or >120%
- Violation of assessment of efficacy parameter
- Violation of visit scheduling.

A subject will be considered non-compliant for the overall study treatment if the subject is non-compliant in Part A.

8 DEMOGRAPHIC AND OTHER BASELINE CHARACTERISTICS

Demographics and baseline characteristics will be summarized with descriptive statistics using the safety population. The list of demographics and baseline characteristics to be summarized will include:

- Age (years) – calculated relative to date of consent
- Age (categorical) - <65 and >=65
- Self-Reported Gender
- Ethnicity
- Race
- Baseline Height (cm)
- Baseline Weight (kg)
- Baseline BMI (kg/m²)
- Baseline Extent of Disease (%)
- Baseline hand mTLSS total score
- Baseline hand PGA Score
- Baseline HECSI

PPD	STATISTICAL ANALYSIS PLAN, Version Final 1.0
Protocol Number: ASN002AD-202 V6.0	Sponsor: Asana BioSciences, LLC

- Baseline hand DLQI
- Baseline pain VAS
- Baseline BSA (%) in AD patients
- Baseline vIGA for AD patients
- Biopsy collection Status

A listing of all demographics and baseline characteristics will be provided.

9 SURGICAL AND MEDICAL HISTORY

Medical and surgical history will be coded according to the Medical Dictionary for Regulatory Activities (MedDRA), Version 21.0

Surgical and medical history will be summarized by system organ class (SOC) and preferred term (PT) using the safety population. A subject who experienced the same surgical and medical history event multiple times will be counted only once for the corresponding PT. Similarly, if a subject experienced multiple surgical and medical history events within the same SOC, the subject will be counted only once for that SOC. Surgical and medical history events will be sorted alphabetically by SOC and within each SOC the PT will be presented by decreasing order.

A listing of all surgical and medical history events will be provided.

10 PRIOR AND CONCOMITANT MEDICATIONS

Medications will be coded according to the World Health Organization Drug Dictionary (WHO-DD), March 2018 B3.

Prior medications are defined as any medications started and discontinued prior to the first study treatment dose. Concomitant medications are defined as any medications taken from the first study treatment dose throughout the end of the study including those started prior to the first study treatment date and continued past that date. See Appendix 2 for handling of completely or partially missing dates for prior and concomitant medications.

Incidence of prior medications will be tabulated by Anatomical Therapeutic Chemical Classification System (ATC) level 3, and PT using the safety population. Incidence of concomitant medications will be tabulated in the same way but presented separately for Part A and Part B using

PPD	STATISTICAL ANALYSIS PLAN, Version Final 1.0
Protocol Number: ASN002AD-202 V6.0	Sponsor: Asana BioSciences, LLC

the safety population. Concomitant medications for Part A are defined as any medications taken after the first dose of treatment and on or before or at week 16 visit, including those that started prior to the first dose of treatment date and continued past that date. Concomitant medications for Part B are defined as any medications taken after week 16, including those started prior to week 16 and continued past that date. A subject with the same medication taken multiple times will be counted only once for the corresponding PT. Similarly, if a subject has taken more than one medication within the same ATC level, then the subject will be counted only once for that ATC.

A listing of all prior and concomitant medications will be provided.

